9.3. Prior and Concomitant Medications

For each participant, medications will be recorded from the date of informed consent/assent through the end of the study (i.e., the EOS visit or, for participants who do not complete the EOS visit, the last available study visit). Medications will be coded using the World Health Organization-Drug Dictionary (WHO-DD).

Prior medications are defined as any medication with start date prior to the date of administration of the first dose of study drug. Per the CCG for this study, all medications given within the 12 months prior to the screening visit will be collected.

Concomitant medications are defined as any medication taken at any time on or after the date of administration of the first dose of study drug through the end of the study. Thus, concomitant medications include (i) medications with start date on or after the date of administration of the first dose of study drug and (ii) prior medications indicated as ongoing or with end date on or after the date of administration of the first dose of study drug. Concomitant medications will be further classified as follows:

- Concomitant medications taken during the 24-52-week treatment period are those medications taken at any time from the date of administration of the first dose of study drug up to the date of the EOT visit (or, if the EOT visit was not performed, the minimum of the date of administration of the last dose of study drug + 14 days and the date of patient last contact).
- Concomitant medications taken during the follow-up period are those medications taken at any time on or after the EOT visit (or, if the EOT visit was not performed, on or after the date of administration of the last dose of study drug + 15 days) through the date of patient last contact.

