- Impute the AE start date as the date of the first dose of study drug. If this results in a date after the AE end date, impute the AE start date as the AE end date instead.
- The imputation flag is set to “Y”.

Adverse Event End Date

The general recommendation is to not impute the AE end date. However, since the AE end date will be used in the programming logic for the imputation of the AE start date, the following intermediate steps will be used.

If the AE end day is missing and the AE end month and year are not missing:

- Impute the AE end day as the last day of the month. If this results in a date after the date of last patient contact, impute the AE end date as the date of last patient contact instead.

If the AE end month is missing and the AE end year is not missing:

- Impute the AE end day and month as “31 December”. If this results in a date after the date of last patient contact, impute the AE end date as the date of last patient contact instead.

If the AE end year is missing:

- Impute the AE end date as the date of last patient contact.

Only the original character/numeric AE end date recorded in the Adverse Event eCRF will be kept in the final analysis dataset (i.e., imputed AE end dates will not be retained in the final analysis dataset).

Prior and Concomitant Medications Data Analysis Conventions

To determine whether a medication is a prior (i.e., pre-treatment) medication or a concomitant medication (or both), incomplete medication start dates will be imputed to be as early as possible and incomplete medication end dates will be imputed to be as late as possible. If the medication start/end date is not complete, then, in the analysis dataset, the character variable will keep the original incomplete date, the numerical date variable will be imputed, and an imputation flag will be derived to indicate which date component is missing.

Prior Medication Start Date

If the medication start day is missing and the medication start month and year are not missing, impute the medication start day as “01”. The imputation flag is set to “D”.

If the medication start month is missing and the medication start year is not missing, impute the medication start day and month as “01 January”. The imputation flag is set to “M”.

If the medication start year is missing, impute the medication start date to be 1 year prior to the date of initial informed consent/assent. The imputation flag is set to “Y”.

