Note: For medications with missing start year, the general recommendation is to not impute the medication start date. However, to simplify the programming logic, the imputation proposed is aligned with the CCG, which specifies to collect all medications given within 12 months prior to the screening visit.

Prior Medication End Date

If the medication end day is missing and the medication end month and year are not missing, impute the medication end day as the last day of the month. If this results in a date on or after the date of the first dose of study drug, impute the medication end date as the date of the first dose of study drug -1 instead. The imputation flag is set to “D”.

If the medication end month is missing and the medication end year is not missing, impute the medication end day and month as “31 December”. If this results in a date on or after the date of the first dose of study drug, impute the medication end date as the date of the first dose of study drug -1 instead. The imputation flag is set to “M”.

If the medication end year is missing, impute the medication end date as the date of the first dose of study drug -1. The imputation flag is set to “Y”.

Concomitant Medication Start Date

The rules for imputing the concomitant medication start date are the same as those described above for imputing the AE start date.

Concomitant Medication End Date

If the medication end day is missing and the medication end month and year are not missing, impute the medication end day as the last day of the month. If this results in a date after the date of last patient contact, impute the medication end date as the date of last patient contact instead. The imputation flag is set to “D”.

If the medication end month is missing and the medication end year is not missing, impute the medication end day and month as “31 December”. If this results in a date after the date of last patient contact, impute the medication end date as the date of last patient contact instead. The imputation flag is set to “M”.

If the medication end year is missing, impute the medication end date as the date of last patient contact. The imputation flag is set to “Y”.

Medication Coding Data Analysis Conventions

Medications whose ATC level 4 cannot be coded will be summarized by setting ATC4=ATC2. However, these unencoded ATC level 4 records need to be confirmed with the study data manager and medical director.

Potentially Clinically Significant Values Data Analysis Conventions

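### SAP 11.2 gives two end-date rules with opposite results, and no stated precedence, for a medication started before first dose with a partial end date

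*SAP*

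**What the plan says.** SAP 9.3 defines a prior medication by its start date alone: "Prior medications are defined as any medication with start date prior to the date of administration of the first dose of study drug". The same section counts as concomitant "prior medications indicated as ongoing or with end date on or after the date of administration of the first dose of study drug". One record can therefore be both.

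SAP 11.2 gives the purpose of the date imputation: "To determine whether a medication is a prior (i.e., pre-treatment) medication or a concomitant medication (or both". Its general principle is that "incomplete medication end dates will be imputed to be as late as possible". It refers to a single imputed numerical date variable and keeps the original partial date as a character value.

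Two specific end-date rules follow in SAP 11.2:

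- **Prior Medication End Date.** With the day missing, use the last day of the recorded month. With the month missing, use 31 December. Both branches then test whether the result falls on first dose or later and, where it does, say to "impute the medication end date as the date of the first dose of study drug -1 instead". For a missing year: "If the medication end year is missing, impute the medication end date as the date of the first dose of study drug -1".
- **Concomitant Medication End Date.** The same late date is used, but the limit is last contact: "If this results in a date after the date of last patient contact, impute the medication end date" (moved back to last contact). With the year missing, the last-contact date is used directly.

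**The concern.** The reset in the prior rule does not ask whether the recorded month or year already lies after first dose. Where it does, the rule returns a date that the recorded data rule out. It also works against the stated principle, because it replaces the latest possible date with one before first dose. And it removes the overlap that SAP 9.3 sets up.

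Records of this kind are to be expected. Patients on oral corticosteroids at baseline are tapered starting 4 weeks after randomization (Protocol 8.2 and Appendix A). Oral antifungals taken at baseline may be stopped during treatment for listed reasons (Protocol 6.1 and 8.2). Both are drugs started before first dose and stopped on study, and a reader of the report will want to see their on-study use. At stake is whether such use appears in the concomitant-medication tables of SAP 9.3 when the stop date is incomplete.

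**Working it through.** The plan gives no figure on this point, so the check applies the two rules as written.

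Let F be first dose, C last contact, and L the latest date compatible with the recorded partial end (last day of the month, or 31 December).

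- Prior rule: end = L if L < F; end = F − 1 if L ≥ F, or if the year is missing.
- Concomitant rule: end = min(L, C); end = C if the year is missing.
- Concomitant status under SAP 9.3: end ≥ F.

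For a medication started before first dose, with assumed dates F = 15 January 2022 and C = 1 December 2022:

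| Recorded end | L | Prior rule | Concomitant rule | On-study use |
|---|---|---|---|---|
| December 2021 | 31 Dec 2021 | 31 Dec 2021 | 31 Dec 2021 | none |
| January 2022 | 31 Jan 2022 | 14 Jan 2022 | 31 Jan 2022 | unknown |
| March 2022 | 31 Mar 2022 | 14 Jan 2022 | 31 Mar 2022 | known |
| 2022 | 31 Dec 2022 | 14 Jan 2022 | 1 Dec 2022 | unknown |
| Year missing | – | 14 Jan 2022 | 1 Dec 2022 | unknown |

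The same happens when only the year is recorded and it follows first dose. With F = 15 November 2021, C = 1 September 2022 and recorded end 2022, the prior rule gives 14 November 2021 and the concomitant rule 1 September 2022.

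The result is general. If L < F, the prior rule returns L, which is before F. If L ≥ F, it returns F − 1, also before F. It can never return a date on or after first dose, so under this rule no partial end date can make a medication both prior and concomitant. A grid confirms this: 365 first-dose dates in 2021, 4 end years (2020 to 2023) and 13 month entries (12 months, or month missing) give 365 × 4 × 13 = 18,980 cases, and 0 return a date on or after first dose. In 11,488 of those cases the whole recorded month or year lies after first dose, and all 11,488 are reset to F − 1.

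Size: SAP 9.3 builds the treatment-period table on the full analysis set, about 30 patients per arm, and counts each patient once per medication class. One patient lost from a class row moves it by 1/30 = 3.3 percentage points, and only if that patient has no other concomitant drug in the class. The follow-up table uses the subset who entered follow-up, so its denominator may be somewhat smaller.

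**The case against.** The strongest reply is that the SAP already contains the right rule. The March 2022 example meets the SAP 9.3 test for a concomitant medication on its recorded month, before any imputation, so a programmer may apply the concomitant rule and obtain 31 March. SAP 11.2 also glosses prior as pre-treatment and allows for both classes, which suggests that the prior rule was meant only for use that ended before treatment.

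Part of this stands. A reader might infer that the SAP necessarily turns known on-study medication into prior-only medication. It does not: that follows only if the prior rule governs. But nothing confines the prior rule to drugs known to have stopped before first dose. SAP 9.3 makes the record prior by its start date, one date variable is imputed, and no order between the rules is given. Two stated rules conflict.

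Three further inferences are tempting and not supported:

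- *The rule is circular.* Prior status comes from the start date, and the imputed end date does not alter it. What is missing is precedence.
- *Every pre-Day 1 medication with an incomplete end date is affected.* The reset applies only if L ≥ F or the year is missing. On-study use is known only when the whole recorded period lies after first dose.
- *Intercurrent events of the primary estimand are missed.* SAP 9.3 describes blinded sponsor adjudication of rescue and prohibited medications and does not say that it uses imputed dates. The partial date is retained. A rescue course started on study is not a prior medication, so the prior rule does not reach it.

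**Conclusion.** The point holds as a conflict between two stated rules, of minor severity. For a medication started before first dose whose recorded end month or year lies wholly after first dose, the prior rule gives a date contradicted by the record, and the concomitant rule gives a date consistent with it. If the prior rule governs, known on-study use is lost from the descriptive concomitant-medication tables, by at most 3.3 percentage points per patient in a class row of an arm of 30. The documents do not give the number of such records.

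Complete end dates, records marked ongoing and partial dates wholly before first dose are unaffected. Where the end falls in the first-dose month or year, or the year is missing, on-study use is unknown; there the reset departs from the SAP's own principle but does not contradict the record.

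The primary FEV1 analysis does not change, because SAP 7.2.1.1 uses all data through Week 24 under treatment policy. The antifungal covariate does not change either: it refers to use at screening, and both rules place the end of a reset record after screening. An effect on rescue or prohibited adjudication is not shown. The text of SAP 7.1.5 on corticosteroid dose is withheld, so nothing is claimed about it.

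**What to change.** State in SAP 11.2 that, for any medication started before first dose, the existing Concomitant Medication End Date rule governs whenever the recorded end month or year lies after first dose, so that the record is both prior and concomitant.

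For ends in the first-dose month or year, or with the year missing, choose one of two courses and write it down. Either apply the same concomitant rule, which matches the late-imputation principle, or keep the reset and label it an explicit exception to that principle.

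The cost is a few lines of SAP text and one programming rule, before database lock. Choosing the concomitant rule for the unknown cases may slightly over-count medications as concomitant, which is the direction the SAP's principle already accepts.

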11.3. Data for Non-Efficacy Endpoints

Date of First/Last Study Drug Injection

The date of first study drug injection (equivalently, the date of first dose of study drug administered) is the earliest date of study drug injection among the non-missing, non-zero dosing records documented in the Study Drug Administration eCRF.

The date of last study drug injection (equivalently, the date of the last dose of study drug administered) is the latest date of study drug injection among the non-missing, non-zero dosing records documented in the Study Drug Administration eCRF. If a patient's date of last dose is missing or unknown, his/her last visit date (including phone call visits) up to but not including the EOT visit will be substituted.

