#### 8.4.2. Study Drug Discontinuation

Patients who permanently discontinue from study drug should be encouraged to remain in the study. Those who agree and do not withdraw from the study will be asked to return to the clinic for all remaining study visits per the visit schedule.

Patients who permanently discontinue from study drug and who opt to withdraw from the study will be asked to complete study assessments, per Section 9.1.2.

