5.2. Treatment Period Dispositions

The disposition of all randomized patients during the treatment period will be displayed by treatment group (as randomized). The number of treated patients (i.e., patients who received at least 1 dose of study drug) and the number of patients who complete the treatment period will be presented. A patient is considered to have completed the treatment period if they have an end of treatment (EOT) visit. As patients who discontinue study drug are allowed to remain in the study, the number of treatment period completers who remained on study drug throughout the entirety of the treatment period and those who permanently discontinued study drug early will be reported. Patients who permanently discontinued study drug early will be further summarized by reason for early study drug discontinuation (including COVID-19-related reasons).

The number of treatment period completers who proceed into the follow-up period will be reported. A patient will be considered to have entered the follow-up period if they had an EOT visit and the patient's date of last contact is after the date of the EOT visit. The disposition of patients who enter the follow-up period is described in Section 5.3.

Lastly, the number of patients who discontinue from the study during the treatment period (i.e., who have an early termination visit and no EOT visit in the database) will be presented. Patients who discontinue from the study early will be further summarized by reason for early discontinuation from the treatment period (including COVID-19-related reasons).

Corresponding percentages with respect to the number of randomized patients in each treatment group will also be presented for the aforementioned treatment period disposition statuses.

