9. SUMMARY OF EXPOSURE DATA

9.1. Study Drug Exposure and Compliance

Study drug exposure and compliance will be summarized by treatment group for the SAF population.

The duration of exposure to study treatment (in days) during the study will be presented by treatment group and calculated for each individual patient as:

(Date of last study drug administration – date of first study drug administration) + 14 days

The calculation does not take into account temporary dosing interruptions (including dosing interruptions due to COVID-19).

The number and percentage of patients randomized and exposed to double-blind study drug will be presented by the following, cumulative, duration of exposure categories: ≥ 14 days, ≥ 28 days, ≥ 42 days, etc., with a 14-day increment added for each subsequent category. The highest category displayed will account for the maximum duration of exposure observed in the study.

In addition, duration of exposure to study treatment during the study will be summarized for each treatment group by the following summary statistics: arithmetic mean, sample SD, minimum, Q1, median, Q3, and maximum.

Compliance with the study drug will be calculated as follows:

(Number of study drug injections during the exposure period)/(Number of planned study drug injections during the exposure period) $\times 100\%$

The number of study drug doses administered and treatment compliance will be summarized for each treatment group by the following summary statistics: arithmetic mean, sample SD, minimum, Q1, median, Q3, and maximum. Treatment compliance will also be presented by the following ranges: $<80\%$ and $\geq 80\%$.

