10. ANALYSIS OF SAFETY DATA

Summaries of safety results will be presented by treatment group. All clinical safety variables will be analyzed using the SAF.

For safety variables (i.e., adverse events, laboratory measurements, vital signs, physical examination, and electrocardiography parameters), 3 observation periods are defined:

- The pre-treatment period is defined as the time from signing the ICF to prior to the first dose of study drug
- The on-treatment period is defined as the time from Day 1 (on or after administration of the first dose of study drug) to the date of last dose of study drug + 14 days
- The follow-up period is defined as the time from the end of the on-treatment period (i.e., date of last dose of study drug + 15 days) plus 12 weeks (i.e., 84 days)

Additionally, the treatment-emergent period is defined to comprise of the on-treatment and follow-up periods.

To support the assessment of the secondary endpoint of the incidence of treatment-emergent adverse events (TEAEs) from baseline through the end of treatment (week 24-52), summary tables will be provided for AEs that occur during the on-treatment period. A separate set of summary tables will be provided for AEs that occur during the on-treatment or follow-up safety periods (i.e, during the treatment-emergent period).

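### SAP 11.3 can place an unknown last-dose date well after a patient stopped drug, because the fallback ignores permanent discontinuation

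*SAP*

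**What the plan says.** SAP 11.3 first defines the last injection as "the latest date of study drug injection among the non-missing, non-zero dosing records documented in the Study Drug Administration eCRF". If the patient's last-dose date is missing or unknown, "his/her last visit date (including phone call visits) up to but not including the EOT visit will be substituted". The rule does not refer to permanent discontinuation of study drug.

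Patients who stop drug are expected to stay. Protocol 8.4.2: "Patients who permanently discontinue from study drug should be encouraged to remain in the study". SAP 5.2 plans for this ("As patients who discontinue study drug are allowed to remain in the study") and reports completers who stopped drug early separately. Protocol 9.1.4 times EOT for these patients at two weeks after their last visit, not after their last dose.

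The last-dose date is then used in three places:

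- **Exposure (SAP 9.1):** last dose minus first dose, plus 14 days.
- **Compliance (SAP 9.1):** injections received divided by "Number of planned study drug injections during the exposure period", reported as below 80% or at least 80%.
- **On-treatment period (SAP 10):** runs from Day 1 "to the date of last dose of study drug + 14 days". In support of the secondary endpoint on treatment-emergent adverse events, "summary tables will be provided for AEs that occur during the on-treatment period". The follow-up period is anchored to the same date.

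**The concern.** Using the last visit before EOT as a stand-in for the last dose is sensible for someone still being dosed every two weeks. For a patient who stopped drug and kept attending visits or taking calls, that visit can fall long after dosing ended. Time off drug is then counted as exposure, adverse events from that time enter the on-treatment tables, and the planned-injection count grows while the received count does not. A patient who took every injection until stopping could be reported below 80%.

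A missing date is conceivable. The protocol's schedule of events allows injections at home and includes a paper home-dosing diary.

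**Working it through.** **Inputs.** The exposure formula and on-treatment window are from SAP 9.1 and 10. Dosing is every two weeks (Protocol 8.1), with a loading dose of 600 mg given as 300 mg syringes, so two injections on Day 1. Treatment lasts 24 to 52 weeks (SAP 1.1), with about 30 patients per arm (Protocol 7.1). Nominal visit day is 7 × week + 1. For a patient off drug, the last visit before EOT is taken as two weeks before EOT.

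**Check of the formula against the plan.** Last dose at Week 22 (Day 155): (155 − 1) + 14 = 168 days = 24 weeks. Last dose at Week 50 (Day 351): (351 − 1) + 14 = 364 days = 52 weeks. Both match the stated limits.

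**Excess exposure if the fallback is used.** The on-treatment window lengthens by the same number of days.

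| True last dose | EOT | Substituted date | Exposure by rule | True exposure | Excess (days) |
|---|---|---|---|---|---|
| Week 22 (Day 155) | Week 24 | Day 155 | 168 | 168 | 0 |
| Week 8 (Day 57) | Week 24 | Day 155 | 168 | 70 | 98 |
| Week 8 (Day 57) | Week 36 | Day 239 | 252 | 70 | 182 |
| Week 8 (Day 57) | Week 52 | Day 351 | 364 | 70 | 294 |
| Day 1 | Week 52 | Day 351 | 364 | 14 | 350 |

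**Windows, Week 8 stop and Week 52 EOT.** The on-treatment period ends on Day 351 + 14 = 365 instead of Day 57 + 14 = 71. The end of follow-up moves from Day 57 + 15 + 84 = 156 to Day 351 + 15 + 84 = 450.

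**Compliance, Week 8 stop.** Injections received: 5 dosing visits + 1 = 6. True compliance is 6/6 = 100%. With EOT at Week 24, planned injections are 12 + 1 = 13 and compliance is 6/13 = 46%. With EOT at Week 52, they are 26 + 1 = 27 and compliance is 6/27 = 22%.

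**Effect on an arm of 30.** One affected patient raises mean exposure by 98/30 = 3.3 days or 294/30 = 9.8 days in the two Week 8 cases, and by 350/30 = 11.7 days at most.

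**If the missed-dose sentence applied.** Protocol 8.4.2.2 says a patient who misses more than four doses in a row is discontinued from the study. After a last dose at Week 8, the fifth missed dose is at Week 18 (Day 127). Taking that as the last visit, the excess is 127 − 57 = 70 days, and compliance is 6/(10 + 1) = 55%.

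**When the fallback is used.** SAP 11.3 can be read in two ways:

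1. Strict: the maximum is taken over dated records, so any patient with at least one dated injection has a last-dose date. The fallback is then left for patients with no dated injection, and almost never applies.
2. Wider: an undated final record makes the last-dose date unknown even though earlier injections are dated. The Week 8 examples need this reading, since six injections are known to have been given.

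**The case against.** The strongest reply is that the rule may never affect anyone in this group. The definition takes the latest date among non-missing records before the fallback is reached. A reader might infer that one undated record overrides known injection dates, but SAP 11.3 does not say so; that is only the wider reading. Patients who stay in the study also keep attending clinic visits at which the diary is reviewed, and accountability records must carry dates (Protocol 8.9.3). A lost date is more natural in someone lost to follow-up, for whom the last visit is a reasonable stand-in. This stands, and it limits how often the problem can arise.

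Second, a reader might take the 294-day case as typical. It is near the upper end, and it could not arise if the missed-dose sentence in Protocol 8.4.2.2 governed everyone. That sentence sits under temporary discontinuation and conflicts with Protocol 8.4.2 and SAP 5.2; these passages must be reconciled. Even with it, about 70 excess days remain.

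Third, counting doubtful events as treatment-emergent is a common cautious convention, the secondary endpoint is worded as running to the end of treatment, and each patient counts once per event. So the adverse event tables would change by at most one patient per cell for each affected patient. That is fair, but it does not defend overstated exposure or understated compliance. Elsewhere in SAP 11.2, imputed adverse event and concomitant medication end dates are capped at last contact, and imputed medication dates are flagged. The last-dose rule has no cap tied to discontinuation and no flag.

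**Conclusion.** The rule as written gives a wrong last-dose date for a patient who has permanently stopped drug, stays to a later EOT and has an unknown last-dose date. Exposure and the on-treatment window are then too long by 0 to about 350 days, depending on the stop and EOT dates, and compliance is too low.

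The size rests on nominal visit days and on the fallback being triggered. On the strict reading that almost never happens. The documents do not give the number affected, and it may be zero.

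The documents do not support a conclusion that the trial's safety results will be distorted. Nor are the main efficacy results at risk: the primary FEV1 model (SAP 7.2.1) does not use the last-dose date, and the exacerbation offset (SAP 7.2.2) runs to EOT or last contact. This is a minor correction to a stated rule, worth making because it costs almost nothing.

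**What to change.** In SAP 11.3:

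- State whether an undated final dosing record triggers the fallback when earlier injections are dated.
- For patients with a recorded permanent discontinuation of study drug, cap the substituted date at that discontinuation. If its date is not held, use the last dated injection.
- Never set the substitute earlier than the last dated injection.
- Keep the present rule for patients with no recorded discontinuation.
- Flag every substituted date in the analysis dataset.

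The remaining error is small. If the Week 8 injection is undated and the last dated one is Week 6 (Day 43), exposure is (43 − 1) + 14 = 56 days against a true 70, so 14 days short.

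Separately, the sentence on more than four missed doses in Protocol 8.4.2.2 must be reconciled with Protocol 8.4.2 and SAP 5.2.

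The SAP 11.3 change costs one sentence and a few lines of code. SAP 5.2 already tabulates permanent discontinuation by reason, but the documents do not show whether an exact discontinuation date is held, hence the second option in the cap.
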